## 4.3 EXCLUSION CRITERIA

### 4.3.1 Patient participants

- We will exclude any patient who is expected to die imminently, as per clinical opinion.
- We will exclude any patient where mobilisation is contraindicated by the nature of their existing injuries.
- Where it is clear from the medical records that participants are prisoners or offenders on probation. This is because of the additional ethical implications of including these patients.
- Patients with neuromuscular disease or acute brain injury or spinal cord injury. Exclusion of this group is firstly because early rehabilitation of stroke patients is associated with worse outcomes (Avert Group, 2015, Cuthbertson and Goddard, 2017) and secondly because mobilisation of these patients is much more complex.
- If the patient and/or their consultee is unable to speak English. Spoken English is required for consent and outcome measurement and there is not provision for an interpreter.

### 4.3.2 Clinician participants in either the survey on acceptability of randomisation or the survey on feasibility of adverse event tool

No exclusion criteria.

## 4.4 WITHDRAWAL CRITERIA

If participants withdraw their consent, we will not collect further data about them. We will ask the participant's permission for data already collected to be kept and used in the analysis.

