Patient-reported outcome measures (questionnaires) will either be carried out over the phone, by post, or in person (e.g. if the participant is still an in-patient at the hospital site). The performance-based outcome will be carried out at the site and reasonable travel expenses reimbursed for participants as appropriate. Outcomes will be recorded as soon after day 60 as possible, with exact time to follow-up being recorded to inform the feasibility of doing so.

Feasibility of outcome measurement will be primarily assessed by the follow-up rate. Other measures of feasibility will include: number of patients where all outcomes are completed plus any reasons why outcomes were not completed, for instance drop out/withdrawal rate, loss to follow up or death. If a participant is deceased at the time of follow-up, then they will still be counted as having completed the other candidate primary outcome measures. The number of patients who completed each individual outcome will also be measured. Measures of central tendency and variability of data for each outcome will inform suitability for future primary outcome measurement and a future sample size calculation for the RCT. Feasibility success for follow-up rate will be 80% minimum (Hodgson et al., 2016). After the 31st May 2019, we will not contact patient participants directly at day 60 follow-up, for example to confirm survival status or to carry out the follow-up questionnaires or walking test. However, in order to maximise participant follow up, we will still confirm survival status by the means set out above that do not involve direct contact with the participant. We will send a letter to patients that we will not follow up in person at day 60, to inform them of the change in study procedures. If retrospective consent has not yet been gained, the letter will be sent to the consultee.

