### **9.2.2 Approaching potential participants**

If inclusion criteria are met and no exclusion criteria are present, potential participants will be directly approached by a member of the clinical research team on the ICU.

Informed consent will be sought from the patient, however because of the nature of their illnesses and treatments on intensive care, there is a potential for a significant proportion not to have capacity to consent. For example, this could be because they have reduced consciousness due to their critical illness or sedation required for mechanical ventilation. In these instances their consultee will be approached instead, then retrospective consent sought from the patient once

they have capacity. This approach will be taken because this is an exploratory study trying to clarify standard care, it is important to gain consent early in an ICU stay so that a full picture of standard care can be gained. Further, our exploratory study is in preparation for a future RCT of ICU mobilisation. Previous trials of ICU mobilisation have tried to start the mobilisation intervention early in an ICU stay. Therefore, for our observational study, when assessing hypothetical acceptability of recruitment for patients, it is important to ask them at an equivalent time in their ICU stay.

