#### 9.2.4 Consultee advice

If the patient lacks capacity to give informed consent, then the advice of a consultee will be sought on whether the patient would want to participate in the study. In the first instance, the research team will try to contact a personal consultee who is able to advise on the views and feelings of the patient. If their advice cannot be sought within a reasonable timeframe, then the advice of a nominated consultee (i.e. an intensive care consultant at the site – who may or may not be directly responsible for the patient, but not part of the study team) will be sought.

The consultee will initially be approached with a consultee information sheet, the principles of consent will as outlined above and consultee advice will be recorded on a consultee declaration form. If the personal consultee is found after a nominated consultee has signed a consultee declaration form, then the personal consultee's advice will be sought. If the participant is conscious, but does not have capacity, efforts will be made to provide verbal information to them about the research study. If participants appear to object to any study procedures, then their consultee's advice will be sought over whether to continue their participation in the study. If it is clear from the consultee or from the ICU case notes that there is an advanced decision or statement by the participants that makes it clear they would oppose taking part in the research, then their participation will not be sought.

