#### 9.2.5 Retrospective consent from the patient

If consultee advice has been gained for a participant, but then the participant regains capacity, then they will be informed of their current participation in the study, then retrospective consent will be sought from them, following the principles outlined above. If the participant wishes to withdraw from the study, we will not collect further data about them. We will ask the participant's permission for data already collected to be kept and used in the analysis. There may be cases where retrospective consent is sought at day-60 follow up. If the participant is physically present at the research site for follow up (for example they are returning to the site to complete the follow up walking test), then written consent will be sought as described above. If the participant is not present at the research site at follow up (for example they are unable to complete the walking test but wish to complete the follow up questionnaires over the phone) then verbal retrospective consent will be sought (and we will offer to post a copy of the retrospective participant information sheet). As outlined above, after 31st May 2019, day 60 follow up involving direct contact with the participant will not be carried out. Therefore, for participants where day 60 occurs after this date, we will continue to seek retrospective consent whilst they remain an in-patient at the research site.

If the participant/consultee is unable to read the information sheet in English, they will not be recruited as there is no financial provision for translators.

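### The single withdrawal rule in sections 4.4 and 9.2.5 ends record-based data collection as well as contact, and offers no lesser level that a participant could agree to

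*Combined protocol and SAP*

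**What the plan says.** Section 4.4 gives one withdrawal rule: "If participants withdraw their consent, we will not collect further data about them". Data gathered before that point are not lost automatically: "We will ask the participant's permission for data already collected to be kept and used in the analysis". Section 9.2.5 applies the same rule where a participant enrolled on consultee advice regains capacity and is asked for retrospective consent: "If the participant wishes to withdraw from the study, we will not collect further data about them".

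That step may be common, because section 9.2.2 expects that "there is a potential for a significant proportion not to have capacity to consent". It may also come late: "There may be cases where retrospective consent is sought at day-60 follow up". Under section 9.2.4, a participant without capacity who seems unwilling is not treated as withdrawn at once; "then their consultee's advice will be sought over whether to continue their participation in the study".

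Section 5.6 describes how survival can be established from Trust systems, NHS Spine or the GP. For participants whose day 60 falls after 31 May 2019, it drops direct contact but keeps this route: "we will still confirm survival status by the means set out above that do not involve direct contact with the participant". The section makes no such provision for people who withdraw. It does list withdrawal in the follow-up reporting, among "any reasons why outcomes were not completed, for instance drop out/withdrawal rate, loss to follow up or death".

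**The concern.** The burdens on participants named in section 9.1 are the time taken by the initial survey and by the day-60 measures, above all the return visit for the walk test. Reading survival status and ICU data from existing records adds nothing to them. Yet the one withdrawal rule ends both kinds of collection, and the protocol text offers no intermediate level.

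The missing data are unlikely to be a random subset. A participant who dies before regaining capacity never reaches the retrospective consent step, and section 5.6 counts the deceased as having completed the other outcomes. Only survivors with capacity can refuse there. If such participants withdraw before day 60 and are left out of the mortality figure, the deaths stay in while some probable survivors leave. Day-60 mortality is a candidate primary outcome and is meant to inform the sample size of the future RCT (sections 2 and 5.6).

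If withdrawal happens on the ICU, the standard-care outcomes in section 5.5 that fall after it are also lost: the times to sitting out, standing and walking, the ICU Mobility Scale level at ICU discharge, and lengths of stay.

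**Working it through.** **Inputs.** From the documents: a maximum of N = 40 patients (section 6.1) and a follow-up success threshold of 80% (section 5.6). The documents give no expected mortality or withdrawal rate, and there is no figure in the plan to reproduce. Deaths (d), withdrawals before day 60 (w) and other losses (o) below are all assumed.

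**1. The rules side by side.**
- Withdrawn (4.4, 9.2.5): no further data of any kind.
- Day 60 after 31 May 2019 (5.6): no contact, survival still checked from records.
- Had consented, then without capacity at day 60 (9.2.3): no questionnaires or walk test, but kept in the study, because complete exclusion would bias the feasibility results.

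The second and third groups keep record-based status without active follow-up. A withdrawing participant is not offered that, even by agreement.

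**2. Mortality if withdrawn participants are left out.** The documents do not say how withdrawals are handled here, so the exclusion is an inference.
- Status known for all, withdrawn all alive: d/N.
- Withdrawn left out: d/(N − w).
- Bounds with withdrawn status unknown: d/N to (d + w)/N.

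With d = 10 and w = 4: 10/36 = 27.8% against 10/40 = 25.0%, a shift of 2.8 points; bounds 10/40 = 25.0% to 14/40 = 35.0%.

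The direction depends on what happens to the four. If one dies by day 60, the true figure is 11/40 = 27.5%, and 27.8% is about right. If two die, it is 12/40 = 30.0%, and 27.8% is too low.

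Other assumed counts, with all withdrawn participants alive at day 60:

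| d | w | d/40 | d/(40 − w) | Shift (points) |
|---|---|---|---|---|
| 8 | 4 | 20.0% | 22.2% | 2.2 |
| 12 | 2 | 30.0% | 31.6% | 1.6 |
| 12 | 4 | 30.0% | 33.3% | 3.3 |
| 12 | 8 | 30.0% | 37.5% | 7.5 |
| 16 | 4 | 40.0% | 44.4% | 4.4 |

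For scale, the exact 95% interval for 12/40 runs from about 16.6% to 46.5%.

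**3. Follow-up rate.** 80% of 40 is 32, so 40 − 32 = 8 losses are tolerated for all reasons. Each withdrawal kept in the denominator as not followed up costs 1/40 = 2.5 points. With o = 4 and w = 4:
- withdrawals kept as not followed up: 32/40 = 80.0%;
- withdrawals removed from the denominator: 32/36 = 88.9%;
- survival status alone counted as follow-up, and all four agree to the check: 36/40 = 90.0%.

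The same participants give 80.0% or 88.9% according to a denominator that the protocol does not define. The 90.0% applies to mortality only, since a record check yields no questionnaire or walk-test result.

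**The case against.** The strongest reply is that the rule respects the participant's decision and does less damage than it seems to. Someone enrolled on consultee advice who then refuses has never personally consented, so stopping all collection is a defensible ethical choice. The late-enrolled group in section 5.6 had not withdrawn, so it is not a direct precedent. Both points stand, and they are why any continued collection must rest on the participant's agreement.

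Several stronger readings are tempting, and the documents do not support them:

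- *Withdrawn participants vanish from the follow-up results.* They do not. Section 5.6 reports withdrawal as a reason for non-completion, and section 5.1 records numbers and reasons at each stage. What is missing is the denominator.
- *They are known to be alive at day 60.* They are known to be alive when they withdraw. For most, day-60 status is unknown. Where refusal comes at the day-60 contact, section 5.6 has survival checked first, so status would normally be on file and could be kept with permission.
- *Declining one survey or visit triggers section 4.4.* Nothing says so. Section 5.6 counts completion of each outcome separately, and section 9.2.5 foresees someone who answers questionnaires by phone without the walk test.
- *All ICU data of a withdrawn participant are lost.* Only data after withdrawal are lost outright; earlier data can be kept with permission.

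It is also fair to say that how often refusal would occur on the ICU is unknown, that the analysis is descriptive, and that in a feasibility study the withdrawal rate is itself a result. The participant documents are not in the text available here, so it cannot be checked whether the forms offer options that the protocol omits.

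**Conclusion.** The point holds as a modest, inexpensive improvement to the design. Sections 4.4 and 9.2.5 state one all-or-nothing rule, and nothing else in the protocol text offers continued record-based collection with agreement. The resulting missing data are avoidable in part and plausibly selected towards survivors.

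The size is small: 2.8 points in the main illustration, and 1.6 to 7.5 points across the other assumed counts shown, against a 95% interval about 30 points wide (46.5 − 16.6 = 29.9). The upward direction rests on two assumptions: that participants who withdraw before day 60 are left out of the mortality estimate, and that fewer of them die by day 60 than among those still observed. A reader might infer a serious bias in mortality, or that a survival check would rescue the 80% criterion. The documents support neither. The check helps only those who agree to it, and it raises follow-up only for the mortality outcome.

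**What to change.** In sections 4.4 and 9.2.5, offer two levels to anyone who withdraws or declines retrospective consent:

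- (a) no further contact, surveys, questionnaires or walk test, but agreement to continued use of routine records and to the no-contact day-60 survival check;
- (b) no further data of any kind, as now.

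Record the level chosen in one CRF field. In section 5.6, state that every enrolled participant stays in the follow-up denominator, with status 'withdrawn' where that applies.

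The cost is wording in the protocol, amended information sheets and consent forms, the CRF field, and one more choice to explain at withdrawal. No extra procedures or staff are needed. Survival status will remain uncertain for those who choose (b).

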## 5. STUDY PROCEDURES

The main data sources will include the routinely collected clinical data contained within the NHS Trust systems, data provided by the participant/their consultee/proxy and data provided by clinicians. Further details and other data sources are outlined below.

### 5.1 PARTICIPANT RECRUITMENT DATA

ICU patients will be recruited as set out elsewhere in this protocol and data about recruitment will be collected:

- Standard recruitment data that records the numbers of individuals at the different stages of the study (for example numbers eligible, numbers excluded) and any reason for not taking part at each stage. This will also include details about any consultee advice given.
- Data to inform which research staff will be required for future recruitment of patients in the RCT will be collected by measuring the number of participants recruited by the clinicians (physiotherapists, doctors or nurses), research nurses or clinician researchers.
- Whether the participant was enrolled before the first mobilisation session has occurred to measure whether this is feasible and the day of ICU stay that consent was obtained.

For each participant enrolled, the following procedures will be carried out (figure 1). In addition, for important feasibility outcomes, we have specified feasibility 'success' criteria which are an indication to consider future investigation of the mobilisation of patients receiving vasoactive drugs. If these criteria are not met, then further consideration is required before deciding whether future investigation of mobilisation of this patient group is needed.

## 5.2 DEMOGRAPHIC DATA

Baseline data will be collected for all participants included in the study in order to provide information on the characteristics of patients potentially eligible for a future RCT. This data will be used to describe baseline characteristics (for example age, gender), characteristics of ICU admission (for example reason for admission, APACHE (Acute physiology and chronic health evaluation) II score (Knaus et al., 1985), SOFA (Sequential Organ Failure Assessment) score (Vincent et al., 1998), and the length of time receiving mechanical ventilation and/or non-invasive ventilation. Contact details of the patient and next of kin will be recorded to facilitate day 60 follow-up.

## 5.3 KEY OUTCOMES

Key outcomes for this exploratory study are:

- Hypothetical recruitment rate for the future RCT.
- Follow-up rate of participants for day-60 outcomes.

More details about these outcomes, plus the secondary outcomes for this study are detailed below.

## 5.4 SURVEY

### 5.4.1 Patient/consultee survey

Once a patient has been recruited into the feasibility study, a short survey will be carried out with the patient, or consultee if they were the one to give 'consent' on behalf of the patient. For a full list of the questions / the form where the information will be logged, please see the 'Patient participant initial survey Case Report Form'. Firstly they will be presented with a summary of the future RCT plus three randomisation scenarios for patients receiving vasoactive drugs: (1) early physical rehabilitation or no rehabilitation; (2) early physical rehabilitation or standard care; or (3) 'protocolised care' (where the decision to mobilise is based on a pre-defined risk stratification protocol – based on the results of the results of a previous Delphi study (IRAS project ID: 212066; REC reference: 17/LO/0830)) or standard care. The following outcomes will then be assessed:

- Acceptability of hypothetical recruitment into the future RCT. This will be measured by a hypothetical recruited rate for the future RCT. Reasons why patients would not consent will also be collected. Feasibility 'success' is defined as two patients per ICU per month (Hodgson et al., 2016)
- Acceptability of hypothetical randomisation into the RCT. This will be measured by the number of feasibility participants who would accept the randomisation scenarios described above and the reasons for their decisions.

Recent evidence has shown how comorbidities (Puthucheary and Denehy, 2015), pre-morbid frailty (Muscadere et al., 2017, Ferrante et al., 2018) and physical function/disability (Ferrante et al., 2015, Biehl et al., 2015) influence long-term physical outcomes and mortality after an ICU admission. As a result, the importance of recording this data for trial participants has been emphasised to ensure that groups are comparable (Azoulay et al., 2017, Connolly and Denehy, 2018). Therefore as part of the above survey, patient co-morbidities (for example using the Functional Comorbidity Index (Groll et al., 2005) and the Charlson Comorbidity Index (Charlson et al., 1987)), pre-morbid frailty (for instance using the Clinical Frailty Scale (Pugh et al., 2018, Rockwood et al., 2005)) and physical functioning (for example using the World Health Organization Disability Assessment Schedule 2.0 (WHODAS 2.0) 36-item or 12-item version (Ustun et al., 2010)) will be measured. The feasibility of measuring baseline comorbidities, frailty and physical functioning through patient or consultee (proxy) reporting or through information contained in the case notes will then be measured by the number of completed outcomes for each patient recruited into the feasibility study. Feasibility 'success' is defined as completing the above

outcomes for 98% of participants. The time point that the above information is collected will also be recorded.

#### **5.4.2 Clinician survey**

For each patient recruited into the feasibility study, ICU clinicians (consultant doctor in charge, nurse in charge and the senior physiotherapist following recruitment) will be presented with a brief outline of the future RCT as well as the randomisation scenarios outlined above. This will occur ad hoc on the ICU following recruitment. For a full list of the questions / the form where the information will be logged, please see the 'Clinician survey on acceptability of randomisation Case Report Form'. The following outcome will be measured:

- Acceptability of hypothetical randomisation into a future RCT. This will be measured by the number of clinicians who would accept the randomisation scenarios described above for each patient recruited into the feasibility study, and the reasons for their decisions. Feasibility success is if 80% of participants are acceptable to be randomised (in whichever scenario). The time point that the clinicians are asked will also be recorded.

#### **5.5 ANALYSIS OF MOBILISATION**

Whenever a physiotherapist reviews a patient recruited into the feasibility study for potential physical rehabilitation whilst they are receiving vasoactive drugs, they will complete an extra proforma in the case notes. This will record the following data to provide information on the decision-making process on the readiness of a patient to mobilise and the feasibility of using an adverse event tool:

- Who made the final decision whether to mobilise the patient and the reasons for the decision.
- Was the presence of vasoactive drugs a factor in the decision of whether to mobilise, either from the perspective of clinicians or in discussion with the patient/family/carers themselves?
- If a mobilisation treatment is carried out the following will also be completed:
  - The reasons why the mobilisation treatment was stopped. This is measured to capture clinicians perceived risk thresholds for discontinuing mobilisation. This informs the measurement of the usability of the adverse event tool.

- An ICU physical rehabilitation adverse event tool used to measure adverse events that occur during or immediately after the mobilisation treatment. This is a new adverse event tool developed by the authors using an international, expert consensus Delphi process (IRAS project ID: 212066; REC reference: 17/LO/0830). The tool outlines specific adverse events including cardiovascular, respiratory, neurological, airway, attachments, falls and injury related events agreed as important to record when measuring the safety of ICU mobilisation.
- The approximate time taken to complete the adverse event tool to inform the assessment of its feasibility. Feasibility success is defined as less than 5 minutes

Alongside this, a case note review will be completed by the research team for each mobilisation treatment of patients receiving vasoactive drugs enrolled into the feasibility study. The researcher will record ICU physical rehabilitation adverse events and serious adverse events that occur during or immediately after mobilisation treatment. The following outcomes will then be measured:

- ICU rehabilitation adverse event rate and SAE rate. SAEs will be measured during the note review and as reported by clinicians and researchers during the study as part of the mandated safety reporting. This will highlight the most efficient way to collect SAEs and both measures will inform a description of the safety of usual care.
- Description of the number and type of rehabilitation adverse events and serious adverse events. Recorded to measure whether the rehabilitation AE tool is fit for purpose and able to capture all unsafe events that occur in this population of patients mobilising on vasoactive drugs.
- Description of number and type of rehabilitation adverse events recorded prospectively by the treating clinician and retrospectively by researcher case note review. This data will provide information on the usability of the tool and the most feasible way to record AE's in future research.
- Loss of information that occurs when the ICU rehabilitation AE tool is completed by clinicians and researchers will also be recorded to provide feasibility data. For clinicians this will be assessed by the number of mobilisation treatments on vasoactive drugs occurring in patients recruited into the feasibility study where the rehabilitation adverse event tool is not completed or incomplete. For researchers, this will be assessed by the number of mobilisation treatments on vasoactive drugs where the researcher was unable to complete tool using the information available in the case notes. Feasibility success is less than or equal to 10% loss of information.

Towards the end of the data collection period for patients on ICU, a short survey will be carried out of clinicians who completed the ICU rehabilitation adverse event tool. This survey will ask about the usability and feasibility of completing the AE tool in the context of clinical practice.

In addition to the above, the following data will be recorded for participants to further quantify standard care:

- Amount of time the patient received vasoactive drugs during the admission.
- Mobilisation occurring whilst patients are receiving vasoactive drugs, for example, by:
  - Number of patients who are mobilised whilst receiving vasoactive drugs.
  - Number of mobilisation treatment sessions on vasoactive drugs.
  - Number of days on vasoactive drugs where mobilisation treatment occurred.
  - Highest level of mobilisation achieved in each treatment session using the ICU Mobility Scale (IMS) (Hodgson et al., 2014a, Tipping et al., 2016).
  - Type and dose of vasoactive drugs patient received during mobilisation treatment.
- Patients receiving vasoactive drugs who are not mobilising, for example, by:
  - Number of days receiving vasoactive drugs where mobilisation is not occurring.
  - On these days, any documented reasons for not mobilising.

The following outcomes will be used to describe standard care, for potential use as surrogate outcomes in a future pilot trial or feasibility study:

- Time to first mobilisation treatment and whether this first mobilisation treatment occurred whilst the patient was still receiving vasoactive drugs.
- Time to first being able to sit out of bed, stand and walk (regardless of the assistance required) (Nickels et al., 2017, TEAM Study Investigators et al., 2015).
- ICU Mobility Scale (IMS) level at ICU discharge.
- ICU and hospital length of stay.

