### **Primary objective 2**

**To describe the preliminary feasibility of measuring the safety of mobilising ICU patients receiving vasoactive drugs.**

#### Secondary objectives

##### 2 a) Recruitment

1. To measure the number of patients who would consent in principle to be recruited into an RCT on the safety of mobilising patients receiving vasoactive drugs and to describe the reasons why patients would not consent.
2. To understand the acceptability to patients and clinicians, of randomising patients receiving vasoactive drugs to an intervention or control arm in a future RCT on the safety of mobilising patients receiving vasoactive drugs.
3. To test the feasibility of clinicians and clinician researchers taking informed consent from patients or their consultees on ICU.

2 b) Sample size

1. To measure mortality, disability, physical functioning and health related quality of life outcome measures of ICU patients to inform a future sample size calculation.

2 c) Outcomes

1. To describe the feasibility of measuring mortality, physical functioning, disability and health related quality of life outcomes to inform a future primary outcome choice.
2. To measure whether an adverse event tool captures all unsafe events that occur during or immediately after early mobilisation of adult intensive care patients receiving vasoactive drugs.
3. To describe the feasibility of an adverse event tool, during clinical practice by ICU clinicians and retrospectively by researchers.

[figure not shown]

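### Section 5.5 scores the researcher's case note review on notes that also hold the clinician's adverse event form, without separating the two, so the comparison of recording routes can be contaminated

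*Combined protocol and SAP*

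**What the plan says.** Section 5.5 describes two ways of recording adverse events for the same mobilisation treatments.

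- **Clinician route.** When a physiotherapist reviews an enrolled patient who is on vasoactive drugs, "they will complete an extra proforma in the case notes". If a treatment takes place, the new adverse event tool is one of the items on that form.
- **Researcher route.** In parallel, "a case note review will be completed by the research team for each mobilisation treatment" given on vasoactive drugs to enrolled patients.

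Information loss is then defined for each route. For clinicians it counts treatments "where the rehabilitation adverse event tool is not completed or incomplete". For researchers it counts treatments where "the researcher was unable to complete tool using the information available in the case notes". One sentence after both definitions sets the limit: "Feasibility success is less than or equal to 10% loss of information".

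The same section describes the events "recorded prospectively by the treating clinician and retrospectively by researcher case note review", and says this will inform "the most feasible way to record AE's in future research". In Section 2, the third objective under 2 c) asks about the "feasibility of an adverse event tool, during clinical practice by ICU clinicians and retrospectively by researchers".

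**The concern.** A clinician's form that sits in the case notes is, on the plain wording, part of the information available there. Section 5.5 does not tell the reviewer to ignore it, to read it last, or to record which items came from it. Two reviewers could both follow the definition and report different loss figures: one works from routine charting, the other reads the completed form.

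The plan wants to learn how well each route works by itself. If future research relied on retrospective review alone, there would be no clinician-completed tool to read. A loss figure that draws on the form does not show what that option would achieve. The event counts have the same weakness, because agreement that comes from reading the form says nothing about what routine notes capture. Which route this would favour is not known.

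**Working it through.** **The plan's own figure.** The 10% limit is stated without a derivation, so there is nothing to reproduce. The check is whether the researcher measure can be read independently of the clinician measure.

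**Step 1: logic, with no assumed rates.** Suppose the reviewer uses every completed form. The researcher then fails on a treatment only if the form is missing or incomplete *and* the routine notes are insufficient. Those treatments are a subset of the ones counted as clinician loss, so researcher loss cannot exceed clinician loss. If the 10% limit is applied to each route, a clinician pass implies a researcher pass, however poor the routine notes are. If only some forms are used, the subset relation no longer has to hold, but each form used can only lower researcher loss.

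**Step 2: inputs for size.** The documents give none of these, so all are assumed:
- c = share of treatments with a completed clinician form
- r = share of treatments for which routine notes alone suffice
- u = share of completed forms that the reviewer uses

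**Step 3: formulas.**
- Loss from routine notes alone: 1 − r
- Full use, independence: (1 − c)(1 − r)
- Full use, any dependence: from max(0, (1 − c) + (1 − r) − 1) to min(1 − c, 1 − r)
- Partial use, independence: (1 − r)(1 − uc)
- Share of forms needed to bring loss down to 10%: u = (1 − 0.10/(1 − r))/c

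**Step 4: results.**

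| c | r | Routine notes alone | Full use, independence | Full use, any dependence | u needed for 10% |
|---|---|---|---|---|---|
| 90% | 60% | 40% | 4% | 0–10% | 83% |
| 90% | 80% | 20% | 2% | 0–10% | 56% |
| 90% | 85% | 15% | 1.5% | 0–10% | 37% |
| 80% | 60% | 40% | 8% | 0–20% | 94% |
| 70% | 60% | 40% | 12% | 0–30% | not reachable (107%) |
| 90% | 90% | 10% | 1% | 0–10% | none: already met |
| 90% | 95% | 5% | 0.5% | 0–5% | none: already met |

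First row in full: (1 − 0.9)(1 − 0.6) = 0.1 × 0.4 = 0.04, and u = (1 − 0.10/0.40)/0.9 = 0.75/0.9 = 0.833. Half use in that row gives 0.4 × (1 − 0.5 × 0.9) = 0.4 × 0.55 = 0.22, a fail.

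**Step 5: chance of meeting the limit.** The number of treatments is also assumed. With c = 90% and r = 80%, the exact binomial chance of observing at most 10% loss in 20, 40 or 80 treatments is 0.993, 0.999 or 1.000 with full use (expected loss 2%). From routine notes alone (expected loss 20%) it is 0.206, 0.076 or 0.013. This treats treatments as independent, although one patient may contribute several.

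**Step 6: event counts.** An event that appears only on the clinician's form enters the researcher's count once the form is read. Equally, a form showing no event may shorten the search of the notes. Both bring the two counts closer together. The documents give no event rates, so no size can be attached.

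**The case against.** The strongest reply is that the text already points to two routes. Section 5.5 contrasts prospective with retrospective recording, the objective in Section 2 does the same, and nothing directs the reviewer to copy the form. Completing a tool by transcribing one that is already complete is a strained reading. This stands as evidence of intent. It does not settle the point, because the definition that is scored rests on the notes as a whole, and those include the form.

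A reader might infer that the researcher criterion is simply not separate from clinician completion, or that it is passed automatically. The documents do not support that. It needs all, or nearly all, completed forms to be used, and it needs the single 10% sentence to apply to each route, which the text does not say. The table shows the effect fading with partial use or low completion. No false pass is possible once routine notes suffice for 90% or more of treatments.

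Three further replies stand in part:
- The choice of recording route does not rest on this percentage alone. Section 5.5 also measures completion time against a 5-minute limit and surveys clinicians about the tool.
- Excluding the form outright has its own bias. If physiotherapists chart on it instead of in the routine notes, loss without the form is overstated. This is why the fix reports both figures.
- Section 9.3.1 is partly redacted and no review form for Section 5.5 is supplied, so a safeguard elsewhere cannot be ruled out.

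**Conclusion.** The point holds as a contamination risk, with medium confidence. To the extent that reviewers use the clinician's form, researcher loss is lowered, the two event counts move towards agreement, and the comparison of routes is weakened. The automatic pass is the limiting case: full use of completed forms and a 10% limit applied route by route.

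The size cannot be determined from the documents. On the assumed inputs it ranges from a large understatement (4% against 40%) to no effect on the pass or fail result. The figures show that the mechanism can matter, not that it will.

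The consequences are limited. The outcome is secondary, Section 8 plans descriptive analysis only, clinician loss is reported in its own right, and under Section 5.1 a missed criterion prompts more thought rather than a stop. Hypothetical recruitment and day-60 follow-up, the two key outcomes, are untouched. This is a worthwhile clarification, not a threat to the study.

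**What to change.** In Section 5.5, state that:

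1. the existing reviewer completes the tool from routine clinical entries first, where practicable, and only then opens the study form;
2. the source of each item is recorded;
3. researcher loss and researcher-recorded events are reported both with and without the form, and the retrospective route is judged on the figures without it;
4. the 10% limit applies to each route separately, if that is what is meant.

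Keep all sources for the overall adverse event rate and for checking whether the tool misses any unsafe event.

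The cost is a few lines in Section 5.5, a source field on the review form and a small extra step per treatment. No new patient data and no additional reviewer are needed. The total extra effort cannot be fixed in advance, since Section 6.3 says the frequency of mobilisation is uncertain.

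Two limits remain. The reviewer may see the form in passing, and its existence may change routine charting, so the figure without the form only approximates what routine notes would yield. If sources are mixed and not recorded, that figure may not be recoverable without repeating the review.
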